3.3 Study Stopping Criteria

The study will be stopped if 2 or more subjects experience a serious adverse event, excluding adverse events that would be expected within the context of skin testing or oral food challenge, including medical treatment of clinical reactions during food challenge. Toxicities (section 4.2) and adverse events (section 7.0) are listed below. Monitoring is described in section 8.0.

3.4 Recruitment

Adults with a diagnosis of peanut or tree nut allergy by a board-certified allergistimmunologist will be identified as potential subjects from the allergy clinics and electronic medical record database search at the Johns Hopkins Hospital system. The treating physician will ask potential subjects for permission to be contacted by study personnel. Potential subjects will then be contacted by authorized study personnel and given time to review the study information and consider participation. If necessary, recruitment will be extended to include recruiting from local food allergy support groups and advertising on social media.

4.0 TREATMENT PLAN

4.1 **Treatment Dosage and Administration**

Prior studies in food-allergic subjects suggest that two standard (420 mg) doses (two days) of ibrutinib, an irreversible BTK inhibitor, are sufficient to completely inhibit BAT and suppress food SPT wheal size by an average of 77% (44% of all food SPTs became negative) (16). Additional doses of ibrutinib (up to 7 days) did not offer further suppression of SPTs, and BAT remained completely abolished for the duration of treatment. Therefore, we propose to extend these findings to acalabrutinib, another selective irreversible BTK inhibitor. Ten subjects will take acalabrutinib 100 mg twice daily by mouth (every 12 hours) for 2 days. Each subject will be enrolled for a minimum of 3 months (including the follow-up visit for toxicity monitoring).

Acalabrutinib is approved as a daily medication for another indication, and we propose to use the drug in adults only at its approved oral dosing of 100 mg twice daily for a maximum of two days. Dose limiting events include grade 3 or 4 hematologic events, grade 3 or 4 hepatotoxicity, AST or ALT >3 times normal range, creatinine > 2.5 times normal range. Dose-limiting toxicity (DLT) evaluation will be performed throughout the study.

The capsules should be swallowed intact with water. Subjects should not attempt to open capsules or dissolve them in water. Acalabrutinib can be taken with or without food.

If a dose is missed, it can be taken up to 3 hours after the scheduled time with a return to the normal schedule with the next dose. If it has been > 3 hours, the dose should not be taken and the subject should take the next dose at the scheduled time. The missed dose will not be made up and must be returned to the site at the next scheduled visit.

In healthy volunteers, co-administration with CYP3A inhibitors increased C_{max}, and therefore the drug will not be concomitantly administered with strong inhibitors or inducers of CYP3A.

4.2 **Toxicities and Dosing Delays**

Although toxicity is not expected given that subjects will only receive two days of drug, any subject who receives treatment on this protocol will be evaluable for toxicity. Each subject will be assessed for the development of toxicity according to the Time and Events table (Section 5.4).

At each visit, subjects will be monitored for toxicities. This study will follow the FDA Guidance For Industry ("Toxicity grading scale for healthy adult and adolescent volunteers enrolled in preventative vaccine clinical trials") grading system for adverse events (17). If a subject develops a grade 3 or 4 nausea, vomiting, diarrhea, hematologic toxicity, renal toxicity, or hepatotoxicity, or any other Grade 4 toxicity or unmanageable Grade 3 toxicity, the medication will be stopped. Protocols for specific toxicities are listed below.

Hematological Toxicities: ANC < 1,500/µL or platelets < 100,000/µL will result in discontinuation of protocol therapy.

Renal Toxicity: Creatinine will be monitored per protocol. Creatinine levels >2.5 times the normal limit will result in discontinuation of protocol therapy.

Hepatotoxicity: Grade 3 hepatotoxicity, or an increase in AST or ALT >3 times upper limit of normal, will result in discontinuation in protocol therapy.

4.3 **Concomitant Medications/Treatments**

At the systemic exposure levels expected in this study, acalabrutinib inhibition of CYP metabolism is not anticipated.

However, acalabrutinib is metabolized by CYP3A. Concomitant administration of acalabrutinib with a strong CYP3A and P-glycoprotein (P-gp) inhibitor, itraconazole increased exposure by approximately 5-fold. Conversely, concomitant administration of acalabrutinib with a strong CYP3A inducer, rifampin, decreased acalabrutinib exposure and could reduce efficacy. Consequently, the concomitant use of strong inhibitors/inducers of CYP3A should be avoided when possible.

If medically justified, subjects may be enrolled if such inhibitors or inducers can be discontinued or alternative drugs that do not affect these enzymes can be substituted within 7 days before first dose of study drug.

The effect of agents that reduce gastric acidity (eg. proton pump inhibitors or antacids) on acalabrutinib absorption was evaluated in a healthy volunteer study (ACE-HV-004). Results from this study indicate that subjects should avoid the use of calcium carbonate containing drugs or supplements for a period of at least 2 hours before and at least 2 hours after taking acalabrutinib. Use of omeprazole, esomeprazole, lansoprazole or any

other proton pump inhibitors while taking acalabrutinib is not recommended due to a potential decrease in study drug exposure. However, the decision to treat with protonpump inhibitors during the study is at the investigator's discretion, with an understanding of the potential benefit to the subject's gastrointestinal condition and a potential risk of decreased exposure to acalabrutinib.

Although the effect of H2-receptor antagonists (such as famotidine or ranitidine) on acalabrutinib absorption has not been evaluated, if treatment with an H2-receptor antagonist is required, the H2-receptor antagonist should be taken approximately 2 hours after an acalabrutinib dose.

The following concomitant medications/treatments are not allowed: immunomodulatory therapies, oral corticosteroids within 1 month of study participation; those taking antihistamines must stop these drugs for one week prior to enrollment and must refrain from taking antihistamines during the duration of the study so as not to interfere with SPT responses; and any other prior investigational interventions in the past 6 months.

4.4 **Duration of Therapy**

Treatment will last for 2 days. Reasons the study medication may be discontinued include:

- Intercurrent illness that prevents further administration of treatment;
- Unacceptable adverse event(s);
- Subject decides to withdraw from the study; or
- General or specific changes in the subject's condition render the subject unacceptable for further treatment in the judgment of the investigator.

4.5 **Duration of Follow Up**

Subjects will be followed for 30 days after cessation of acalabrutinib treatment. Subjects will be removed from the rapy when any of the criteria listed in Section 5.5 apply. The Principal Investigator will be notified. The reason for study removal and the date the subject was removed will be documented in the Case Report Form. Subjects removed from treatment for unacceptable adverse events will be followed until resolution or stabilization of the adverse event.

4.6 **Subject Replacement**

Subjects who withdraw voluntarily from the study, but were tolerating the drug will be replaced. Subjects who drop out or miss doses due to toxicity will not be replaced since these subjects will be considered to have experienced a dose limiting toxicity.

5.0 **STUDY PROCEDURES**

5.1 Screening/Baseline Procedures

Assessments performed exclusively to determine eligibility for this study will be done only after obtaining written informed consent. Assessments performed for clinical indications (not exclusively to determine study eligibility) may be used for baseline values even if the studies were done before informed consent was obtained.

All screening procedures must be performed within 14 days prior to baseline SBPCFC. The screening procedures include:

5.1.1 Informed Consent

Informed consent will be obtained per IRB and GCP guidelines.

5.1.2 **Medical history**

Complete medical and surgical history, including history of infections will be obtained.

5.1.3 **Demographics**

Age, gender, race, ethnicity will be obtained.

5.1.4 Review subject eligibility criteria

Subjects will be screened to ensure they meet inclusion and exclusion criteria, including history and prior laboratory testing consistent with a diagnosis of IgEmediated food allergy.

5.1.5 Review previous and concomitant medications

Medications will be reviewed and documented.

5.1.6 Physical exam including vital signs, height, and weight

Vital signs (temperature, pulse, respirations, blood pressure), height, weight and basic full physical exam will be performed by study physicians.

5.1.7 Adverse event assessment

Baseline kidney, liver, and heart function will be assessed. This will include a CMP, CBC, Hepatitis B and C testing, and EKG. See section 6 for Adverse Event monitoring and reporting.

5.1.8 **Hematology**

Baseline CBC will be performed.

5.1.9 Blood draw for correlative studies

See Section 9.0 for details.

5.1.10 Serum chemistries

Comprehensive metabolic panel (CMP) to include: albumin, alkaline phosphatase, ALT/SGPT, AST/SGOT, BUN, creatinine, electrolytes (sodium, potassium, calcium, chloride, bicarbonate), glucose, and total bilirubin.

5.1.11 Pregnancy test (for females of child bearing potential)

See section 3.1.6.1 for definition.

5.1.12 Immunoglobulin levels

Total quantitative immunoglobulins (QUIGs), including IqG, IqA, IqM, and IqE, as well as serum specific IgE for peanut/tree nuts will be monitored

5.1.13 Spirometry

To be performed before SBPCFC if the patient has a history of asthma or exercise-induced bronchospasm.

5.2 **Procedures During Treatment**

Screening/Baseline visit (Visit 1) 5.2.1

Screening:

- · Physical exam, vital signs
- Urine pregnancy test (if applicable)
- CBC w/diff
- CMP
- Hepatitis B and C testing
- Total immunoglobulin levels
- EKG
- Spirometry (only if the subject has a history of asthma)
- SPT to relevant foods, saline and histamine controls
- BAT

Procedures (to be done only if labs and EKG are within normal limits)

• Single-blind placebo controlled oral food challenge (SBPCFC) as below

Microparticle analysis

All oral food challenges shall be performed as single (patient)-blinded, placebocontrolled food challenges (SBPCFC) according to standard published guidelines (18, 19). Placebo challenge and active challenge will be performed in that order on the same day if the subject has no symptoms during the first (placebo) challenge. If a reaction requiring treatment occurs during the placebo challenge, the next challenge should not be performed until the symptoms have subsided. Food challenge to peanut or tree nut protein will be performed according to standard operating procedure as previously published in the food allergy field (15).

Actions to minimize risk of severe allergic reactions during oral food challenge): Prior to the study visit, subjects will be told to contact study staff about asthma and seasonal allergy symptoms, fever, acute infections including upper respiratory infections, rashes, or change in status of chronic medical conditions. Study visits will be rescheduled in the event that any of these occur. Study staff will contact subjects 1-3 days before study visits to inquire about recent symptoms.

All food challenges will be conducted in the Clinical Research Unit within the Johns Hopkins Bayview Hospital. Intravenous access will be obtained before the food challenge begins. Emergency medications (epinephrine, diphenhydramine, cetirizine, albuterol, ranitidine) will be immediately accessible in the subject's room. All SBPCFCs will be conducted by trained personnel and supervised by a clinician with experience in performing SBPCFCs and trained in the treatment of anaphylaxis. Spirometry (assessment of pulmonary function) will be performed prior to the onset of the SBPCFC. Vital signs and pulse oximetry will be obtained at baseline and prior to each dose of the food allergen and g15 minutes thereafter with an observation period of at least 2 hours after the last dose is consumed (longer should a reaction occur). The SBPCFC will begin with a low dose, which will increase incrementally. At physician discretion, based upon history and possible subjective or very mild objective symptoms during a challenge, dosing intervals may be extended. The procedure will be stopped when clear objective symptoms are noted.

Subjects will be discharged after a period of observation appropriate to the nature of the symptoms. They will receive information regarding possible delayed manifestations, emergency contact information and home treatment. All subjects will be provided with an epinephrine auto-injector to take home (if they do not have one already) and instructions on how and when to use it.

After a minimum recovery period of 2 weeks, subjects will then take acalabrutinib as described above, and return on the second day of treatment for Visit 2 (see below).

5.2.2 Visit 2

- Physical exam, vital signs
- Urine pregnancy test (if applicable)
- CBC w/diff
- CMP
- Total immunoglobulin levels
- EKG
- Spirometry (only if the subject has a history of asthma)
- SPT to relevant foods, saline and histamine controls
- SBPCFC (performed as described above)
- Microparticle analysis

5.3 **Follow-up Procedures**

Toxicity monitoring (including hematology, serum chemistries, QUIGs, sslgE) and other study procedures will be repeated at 3 months after cessation of acalabrutinib; if at this time toxicity related lab results are not yet back to baseline, they will be repeated at 6 months.

- Physical exam, vital signs
- CBC w/diff
- CMP
- Total immunoglobulin levels
- SPT to relevant foods, saline and histamine controls
- **BAT**

5.4 **Time and Events Table**

Visit	1	2	3
	Screening / Day 0	Day 2	Follow up (30 days after Visit 2)
Informed Consent	Х		
Skin prick testing	Х	X	Х
Basophil activation test	Х	Х	Х
SBPC food challenge	Х	Х	
History and PE	Х	Х	Х
Toxicity (include DLT) Evaluations	Х	X	Х
CBC	Х	Х	Х
CMP	Х	Х	Х
EKG	Х	Х	
Urine pregnancy test ^b	Х	Х	Х
Microparticle analysis	Х	Х	Х

^b Females of child-bearing potential only

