At Visit 1, after undergoing informed consent, subjects will undergo procedures for assessment of baseline status and eligibility (clinical history and skin prick test ISPT) to peanut and/or tree nuts as well as histamine and saline SPT positive and negative controls, respectively). After eligibility is confirmed, subjects will undergo a single-blind, placebo-controlled graded food challenge (SBPCFC) of up to 4 g of peanut or tree nut protein, administered over escalating doses while being monitored in a clinical research unit (CRU) setting. Prior to the SBPCFC, 30 mL of peripheral blood will be collected for basophil activation testing (BAT), serum specific IqE to peanut/tree nuts and components, as well as toxicity lab testing monitoring. During the food challenge, subjects will be assessed for signs and symptoms of foodinduced anaphylaxis between each dose per food challenge protocol, upon report of any symptoms and should any objective change in clinical status occur. Once a confirmed reaction occurs, the food challenge will be terminated and the reaction treated until it has resolved. Subjects will be discharged from the CRU no sooner than 2 hours after completion of the food challenge. They may be observed longer should a reaction occur at the investigator's discretion. Additional blood will be drawn at fixed intervals for biomarkers of anaphylaxis including mast cell and basophil microparticle analysis. This visit will establish each subject's baseline threshold dose for peanut/tree nut reactivity.

After a minimum of a two-week recovery period, subjects will be given acalabrutinib (four doses of 100 mg of acalabrutinib to be taken orally twice daily) and return for Visit 2 to undergo repeat SPT, SBPCFC, and phlebotomy in an identical manner to Visit 1 to establish each subject's new threshold dose for peanut/tree nut reactivity while on acalabrutinib, which we hypothesize will be higher. At this point of the protocol, acalabrutinib dosing will be stopped. Follow up visits for up to 6 months after cessation of acalabrutinib will be conducted to repeat toxicity labs and skin testing.

At each visit, subjects will be monitored for toxicities, including CBC w/diff, CMP, and pregnancy testing. Prior to drug initiation and at the end of the trial, an EKG will be performed.

STUDY SUMMARY

Title	Preventing Life-Threatening Allergic Reactions with Acalabrutinib, an FDA-Approved BTK Inhibitor			
Protocol Number	MD12042018			
Phase	Phase 2			

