- leukocytes ≥ 3.000/mcL - absolute neutrophil count ≥ 1,500/mcL - hemoglobin ≥ 10 g/dL - platelets ≥ 100.000/mcl

within normal institutional limits - total bilirubin - AST(SGOT)/ALT(SPGT) within normal institutional limits - Creatinine within normal institutional limits

- 3.1.6 Women of child bearing potential must agree to two forms of highly effective contraception (hormonal, device, or barrier method of birth control; abstinence) prior to study entry, for the duration of study participation, and for 7 days following completion of acalabrutinib therapy. Should a woman become pregnant or suspect she is pregnant while participating in this study, she should inform the Principal Investigator and her treating physician immediately.
 - 3.1.5.1 A female of child bearing potential is any woman (regardless of sexual orientation, having undergone a tubal ligation, or remaining celibate by choice) who meets the following criteria:
 - Has not undergone a hysterectomy or bilateral oophorectomy; or
 - Has not been naturally postmenopausal for at least 12 consecutive months (i.e., has had menses at any time in the preceding 12 consecutive months).
- 3.1.7 Ability to understand and the willingness to sign a written informed consent.

Ability to clearly understand and speak English at an 8th grade reading level. For 3.1.8 safety reasons, subjects must speak English due to the anticipated need for clear and timely communication with investigators and the study team in emergency situations, since the investigators and study team are English speaking.

3.2 **Exclusion Criteria**

- 3.2.1 Subjects who have been on immunomodulatory therapies or oral corticosteroids within 1 month prior to study participation will be excluded, and those taking antihistamines must stop these drugs for one week prior to enrollment and must refrain from taking antihistamines during the duration of the study so as not to interfere with SPT responses or clinical responses during SBPCFC.
- 3.2.2 Subjects with symptoms consistent with food reactions other than type 1 hypersensitivity (such as atopic dermatitis, eosinophilic esophagitis and any other non-IgE-mediated food sensitivities) will be excluded.
- 3.2.3 History of allergic reactions to study drug or reactions attributed to compounds of similar chemical or biologic composition to acalabrutinib, including active product or excipients.

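### No repeat pregnancy test is scheduled between Visit 1 and the first acalabrutinib dose, so the pregnancy exclusion is not rechecked before exposure (minor)

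*Combined protocol and SAP*

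**What the plan says.** The Study Schema sets the general rule: "At each visit, subjects will be monitored for toxicities, including CBC w/diff, CMP, and pregnancy testing". The visit lists in Sections 5.2.1 and 5.2.2 and the table in Section 5.4 follow it, with the entry "Urine pregnancy test" at Visits 1 and 2. The table also has one at follow-up, after treatment is over.

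The Visit 1 test is a screening procedure (Section 5.1.11), and Section 5.1 gives the window: "All screening procedures must be performed within 14 days prior to baseline SBPCFC".

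The start of treatment is described twice. Section 5.2.1 says "After a minimum recovery period of 2 weeks, subjects will then take acalabrutinib as described above, and return on the second day of treatment"; that return is Visit 2. The Study Schema gives the same two-week minimum and then says "subjects will be given acalabrutinib (four doses of 100 mg of acalabrutinib to be taken orally twice daily) and return for Visit 2". Section 4.1 gives the regimen: "Ten subjects will take acalabrutinib 100 mg twice daily by mouth (every 12 hours) for 2 days".

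Several safeguards concern pregnancy:

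- Section 3.2.6 excludes pregnant and nursing women.
- Section 3.1.6 requires agreement to two contraceptive methods from before entry until 7 days after therapy. It also says of a woman who is, or suspects that she is, pregnant that "she should inform the Principal Investigator and her treating physician immediately".
- Section 5.5.6 lists pregnancy as a reason for removal.
- The pregnancy-reporting paragraph under Section 8.1.3 requires study drug to be stopped when conception is reported.

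**The concern.** An exclusion made for fetal safety protects only if it is true when exposure starts. Here it is tested at Visit 1, and exposure starts two weeks or more later. Two kinds of pregnancy could pass through a schedule followed to the letter: one too early to show at Visit 1, and one begun in the interval and not suspected. Either would first be tested for once dosing was under way.

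The protocol itself treats the hazard as real. Section 1.2 calls the drug pregnancy category D, and Section 7.1.3 says, on animal evidence, that it may harm the fetus. The participants are adults described in Section 7.1.2 as generally healthy apart from allergic disease, so there is little reason to accept an avoidable fetal exposure. What is at stake is participant safety only.

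**Working it through.** The plan states no figure for this interval, so there is none to reproduce. The check is schedule arithmetic.

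**Inputs**

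- s = days from the screening pregnancy test to the Visit 1 challenge: 0 to 14 (Section 5.1).
- r = days from the Visit 1 challenge to dose 1: at least 14, no maximum stated (Study Schema; Section 5.2.1).
- Regimen: 4 doses of 100 mg, 12 hours apart (Study Schema; Section 4.1).
- Visit 2: treatment day 2 (Section 5.2.1).

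**Step 1. Is any test placed between Visit 1 and dose 1?** The Study Schema, Sections 5.2.1 and 5.2.2 and the Section 5.4 table attach tests to visits only. No visit falls in the interval or on treatment day 1. Section 9.2 implies a dispensing step but describes no check at it. The one assessment that the Study Schema words as preceding drug initiation is the EKG. The answer is no.

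**Step 2. Age of the last scheduled test at dose 1.** Age = s + r.

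- Test on the challenge day, minimum recovery: 0 + 14 = 14 days. This is the floor.
- Test at the start of the screening window, minimum recovery: 14 + 14 = 28 days.
- Test on the challenge day, recovery of 28 days: 0 + 28 = 28 days.

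Either a longer screening lead or a longer recovery makes the test older. Because r has no maximum, neither has the age.

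**Step 3. Doses taken before the Visit 2 test.** Dosing starts on treatment day 1 and the test is on treatment day 2, so at least 1 of 4 doses comes first: 100 of 4 × 100 = 400 mg, or 25%. The Visit 2 test can then avert at most 4 − 1 = 3 doses. The documents give no clock times for dosing or for the visit, so the count cannot be fixed more closely.

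**Step 4. Does another safeguard confirm status before dose 1?**

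- Contraception (3.1.6) lowers the chance of pregnancy but does not test for it.
- The reporting duty (3.1.6) acts once a pregnancy is known or suspected.
- Removal (5.5.6) and stopping drug (8.1.3) act once it is known or reported.
- Section 5.2.1 adds a contact: "Study staff will contact subjects 1-3 days before study visits to inquire about recent symptoms". Its stated purpose is to reduce food-challenge risk, and it is timed to Visit 2. One day before Visit 2 is treatment day 1, so the contact need not come before dose 1.

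None of these confirms that the woman is not pregnant before exposure.

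**The case against.** The strongest reply is that the plan breaks no rule of its own. It excludes pregnancy, tests at Visit 1, requires two contraceptive methods throughout and asks for immediate notice of even a suspected pregnancy. No section promises a test within a set time of dose 1, and how recent a test should be for a two-day course is a matter of judgement. A urine test can also miss a very early conception, so the gain is smallest at the 14-day minimum. All of this stands, and it keeps the point minor. It does not supply a check before exposure. The protocol also retests at Visit 2, so it does not treat contraception alone as enough.

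The Section 5.4 table might seem to answer the point, since it labels Visit 1 as day 0 and Visit 2 as day 2, as if drug followed Visit 1 at once. The Study Schema and Section 5.2.1 both state the two-week minimum, so day 2 is best read as the second treatment day.

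Three stronger readings are tempting and are not supported:

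- A reader might infer that dose 1 depends on the old test alone. It does not, given the contraception and reporting rules.
- A reader might infer from the Study Schema sentence on four doses that the whole course comes before Visit 2, so that the test there averts nothing. Section 5.2.1 places the visit within treatment, and the Study Schema stops dosing at that point. Only the floor of one dose is secure.
- A reader might infer a likely or quantified fetal risk. In Section 7.1.3 the rat findings are at 100 mg/kg/day, a dose that was also toxic to the mothers. They give no rate of harm for a two-day course in women.

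**Conclusion.** The gap is real and minor. Under the schedule as written, the last scheduled pregnancy test is at least 14 days old at dose 1, with no upper limit, and at least one of four doses precedes the next test. This rests on reading the two-week recovery as running from the Visit 1 challenge to the first dose, and on taking the Visit 2 test as done on treatment day 2. It concerns only women of child-bearing potential among 10 subjects and any replacements. The event is unlikely, and no endpoint, sample size, power or analysis is affected.

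**What to change.** In Sections 5.2 and 5.4, require a negative urine pregnancy test for women of child-bearing potential on the day of dose 1, before it is taken, or on the day before. Tie it to dose 1 and not to Visit 2. Do it at dispensing if drug is handed out then. If drug is handed out earlier, supply a home kit and have the result reported to staff before dosing begins; the existing pre-visit contact could carry this if it is timed before dose 1. Keep the Visit 2 test and the contraception rule, because a urine test does not exclude a very early conception. The age of the test at dose 1 falls from at least 14 days to 0 or 1.

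The cost is a small amendment with IRB approval (Section 11.5), one kit per woman concerned (at most 10 for 10 subjects, plus any replacements under Section 4.6) and a short result check. The home-kit route adds kit supply and reliance on a self-reported result. No visit is added.

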Appendix 1: Pill Diary

		монтн				
Sunday	Monday	Tuesday	Wednesday	Thursday	Friday	Saturday
Н	4					
-						L
		L				L

The study coordinator will fill in the month and days.

Please document number of pills and time you took the ibrutinib.

STATISTICAL ANALYSIS PLAN

Study Design and Endpoints

This is an open label study of acalabrutinib in 10 food-allergic adults to determine the effect of pretreatment (100 mg twice daily for 4 doses total) with acalabrutinib on food allergen reactivity in foodallergic subjects. There are 3 planned study visits where endpoint assessments will be collected. The primary endpoint will be assessed at Visit 1 (baseline) and Visit 2 (after acalabrutinib). Secondary and exploratory endpoints will be assessed at Visits 1, 2, and 3 (follow-up).

Primary endpoint: Change in subjects' threshold dose of peanut protein to elicit an objective clinical reaction

Secondary endpoints:

- 1. Change in size of skin prick test wheal
- 2. Change in percent of ex vivo basophil activation to anti-IgE and peanut, as determined by CD63 expression

Safety considerations and toxicity monitoring: Laboratory testing (complete blood counts, serum chemistries) and electrocardiogram

Given the nature of the study, it will be stopped if >50% of patients have a DLT as described in the protocol.

Sample Size and Power Analysis

Sample size was calculated based on the primary endpoint, assuming that the difference in threshold from baseline to after acalabrutinib is normally distributed with a standard deviation of 1.1 natural log units. Therefore, 10 subjects allows for 80% power to detect a 3-fold increase (1.1 natural log units; i.e. 1 food dose escalation) in the threshold food dose, using a paired t test with p<0.05 as an approximation. though non-parametric tests will be utilized in the final analysis if needed.

Data Analysis

As this is an open label trial, each subject's responsiveness will be examined compared to themselves (at baseline) prior to initiation of treatment. Descriptive statistics will be used to analyze endpoints. The primary endpoint will be analyzed by log transformation and paired t test with p value < 0.05, if appropriate. If assumptions for paired t test are violated, a Wilcoxon non-parametric sign test will be used.

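### The four doses that the schema and SAP place before the Visit 2 challenge do not, on an ordinary reading, fit a visit on the second day of treatment (section 5.2.1)

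*Combined protocol and SAP*

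**What the plan says.** The Study Schema describes the treatment step as "four doses of 100 mg of acalabrutinib to be taken orally twice daily) and return for Visit 2", where the skin test, challenge and blood draw are repeated on drug. It then closes treatment: "At this point of the protocol, acalabrutinib dosing will be stopped".

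The SAP, under Study Design and Endpoints, sets out to measure the effect of "pretreatment (100 mg twice daily for 4 doses total) with acalabrutinib". It measures the primary endpoint at baseline and at Visit 2, which it places after the drug.

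Section 4.1 is the only place that fixes the spacing: 100 mg "twice daily by mouth (every 12 hours) for 2 days". The schema and the SAP say twice daily without an interval.

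Section 5.2.1 sets the date of the visit. After at least two weeks of recovery, subjects start the drug and "return on the second day of treatment for Visit 2".

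The Time and Events table in section 5.4 labels Visit 2 as Day 2 and the screening visit as Day 0. No section gives a clock time for the first dose or for the challenge, or states how many doses must have been taken before the challenge may start.

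**The concern.** The schema and SAP put all four doses ahead of the challenge. Section 5.2.1 puts the challenge inside a two-day course, and dosing ends at that visit. A dose still outstanding when the challenge begins can never become pretreatment.

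The number of doses taken by then defines the intervention whose effect the trial reports. There are 10 subjects, no control arm and one on-drug challenge each, so nothing else in the design shows which exposure produced the result. If staff follow section 5.2.1 while the analysis follows the SAP, the report would attribute the change in threshold to a four-dose pretreatment that some or all subjects had not completed.

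**Working it through.** **The plan's own figure.** Section 10.2 and the SAP give 80% power for 10 subjects, an effect of 1.1 and a standard deviation of 1.1 natural log units, using a paired t test at 0.05. The noncentrality is √10 × 1.1/1.1 = 3.16 on 9 degrees of freedom, which gives 80.3% two-sided. The figure reproduces. The dose count is not an input to it, so this point leaves it unchanged.

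**Inputs for the dose count.** Four doses (schema, SAP); 12 hours apart (section 4.1); visit on the second day of treatment (section 5.2.1); no dosing after Visit 2 begins (schema). Clock times are assumed, because the documents give none. A daytime challenge is a reasonable assumption: section 5.2.1 runs the placebo and active challenges on the same day and then requires at least 2 hours of observation.

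**Formula.** Doses fall at 0, 12, 24 and 36 hours. If the challenge starts h hours after the first dose, the number already taken is the smaller of 4 and (whole part of h/12) + 1. Four doses therefore need h of at least 36.

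| First dose | Challenge starts | h | Doses taken |
|---|---|---|---|
| 08:00, day 1 | 10:00, day 2 | 26 | 3 |
| 20:00, day 1 | 10:00, day 2 | 14 | 2 |
| 20:00, day 1 | 10:00, day 3 | 38 | 4 |

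**Range on the second calendar day, challenge starting 08:00 to 16:00.** A first dose at 06:00 to 08:00 gives 3 doses, at 09:00 to 12:00 gives 2 or 3, and at 18:00 to 20:00 gives 2. Outside ordinary hours the count moves further. A 22:00 start with an 08:00 challenge has h = 10 and leaves 1 dose. A start between midnight and 05:00 with an afternoon challenge can reach 4.

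**The reading that reconciles the sections.** Suppose the second day of treatment means hours 24 to 48 after the first dose. Four doses then require a challenge between hours 36 and 48. For an 08:00 start, that window runs overnight, from 20:00 on day 2 to 08:00 on day 3. For a 20:00 start, it runs from 08:00 to 20:00 on the third calendar day, which suits a daytime challenge.

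**The section 5.4 table.** Its Day 0 is the screening visit, which section 5.2.1 places at least two weeks before the drug. Day 2 cannot be counted from that Day 0, so the column does not choose between the readings.

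**The case against.** The strongest reply is that the passages can be made to agree. An evening first dose and a visit in the second 24-hour period give four doses before a daytime challenge. The schema's sentence could also describe what is dispensed, and the same sentence has the threshold measured while the subject is on drug, which suits a visit during treatment. This stands in part: the plan does not necessarily deliver too few doses. But the agreement needs two conditions that no section states, and the dispensing reading does not help the SAP, which calls the four doses pretreatment.

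A reader might infer a fixed shortfall of a quarter to a half of the regimen. The documents do not support that, because the count depends on assumed clock times.

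A reader might also set the half-lives in section 1.2 (0.9 hours for the parent drug, 6.9 hours for the active metabolite) against a varying gap between last dose and challenge, and infer lost effect. That does not follow. The protocol describes the drug as irreversible (section 1.2) and covalently bound to its target (section 9.1), so plasma half-life says little about how long the effect lasts. Sections 1.3 and 4.1 report that ibrutinib beyond two doses added no further skin-test suppression. Those are data on another drug and do not show that two or three acalabrutinib doses equal four. They do give no ground for claiming a loss.

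Finally, a reader might ask for one dose-to-challenge interval for every subject. No section states an interval, so there is nothing there to contradict; it would be a new requirement.

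**Conclusion.** Wrong as written. The schema and SAP put four doses before the primary measurement. Section 5.2.1, at the spacing in section 4.1, ordinarily puts two or three there, if the second day of treatment means the second calendar day, doses are taken at ordinary hours and the challenge is in the daytime. On the unstated evening-start reading the count is four.

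What is established is an inconsistency in the exposure that defines the intervention, and the risk that the SAP's conclusion misdescribes it. No loss of efficacy and no particular increase in variability is shown, and the sample size and stated power are untouched.

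**What to change.** Reconcile the Study Schema, sections 4.1 and 5.2.1, the Day 2 column of section 5.4 and the SAP, so that they agree on how many doses precede Visit 2 and when Visit 2 takes place. The table should also say what its day numbers are counted from. Which schedule applies is for the investigators to decide.

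Add a sentence to the SAP committing to report, for each subject, the number of doses actually taken before the Visit 2 challenge. The Appendix 1 diary already asks for pill count and time, so no new case-report field is needed. Its prompt names ibrutinib, which should be corrected if the entries are to be used. Reporting the count would also cover the missed-dose rule in section 4.1, under which a dose more than 3 hours late is skipped and not made up.

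The cost is a wording amendment and one added line in the analysis plan, with no change to the sample size.
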